### Severity

All non-hematologic adverse events will be graded according to the NCI Common Terminology Criteria for Adverse Events (CTCAE) version 4.0. The CTCAE v4 is available at <http://ctep.cancer.gov/reporting/ctc.html>

Adverse events not specifically defined in the NCI CTCAE will be scored on the Adverse Event log according to the general guidelines provided by the NCI CTCAE and as outlined below.

- Grade 1: Mild
- Grade 2: Moderate
- Grade 3: Severe or medically significant but not immediately life threatening
- Grade 4: Life threatening consequences
- Grade 5: Death related to the adverse event

### Serious Adverse Events

ICH Guideline E2A and the UTSW IRB define serious adverse events as those events, occurring at any dose, which meets any of the following criteria:

- Results in death
- Immediately life-threatening
- Results in inpatient hospitalization or prolongation of existing hospitalization
- Results in persistent or significant disability/incapacity
- Results in a congenital anomaly/birth defect
- Based upon appropriate medical judgment, may jeopardize the subject's health and may require medical or surgical intervention to prevent one of the other outcomes listed in this definition.

Note: A "Serious adverse event" is by definition an event that meets any of the above criteria. Serious adverse events may or may not be related to the research project. A serious adverse event determination does not require the event to be related to the research. That is, both events completely unrelated to the condition under study and events that are expected in the context of the condition under study may be serious adverse events, independent of relatedness to the study itself. As examples, a car accident requiring >24 hour inpatient admission to the hospital would be a serious adverse event for any research participant; likewise, in a study investigating end-stage cancer care, any hospitalization or death which occurs during the protocol-specified period of monitoring for adverse and serious adverse events would be a serious adverse event, even if the event observed is a primary clinical endpoint of the study.

1Pre-planned hospitalizations or elective surgeries are not considered SAEs. Note: If events occur during a pre-planned hospitalization or surgery, that prolong the existing hospitalization, those events should be evaluated and/or reported as SAEs.

- 7.2.2 2 NCI defines hospitalization for expedited AE reporting purposes as an inpatient hospital stay equal to or greater than 24 hours. Hospitalization is used as an indicator of the seriousness of the adverse event and should only be used for situations where the AE truly fits this definition and NOT for hospitalizations associated with less serious events. For example: a hospital visit where a patient is admitted for observation or minor treatment (e.g. hydration) and released in less than 24 hours. Furthermore, hospitalization for pharmacokinetic sampling is not an AE and therefore is not to be reported either as a routine AE or in an expedited report.**Unanticipated Problems Involving Risks to Subjects or Others (UPIRSOs):

The phrase "unanticipated problems involving risks to subjects or others" is found, but not defined in the HHS regulations at 45 CFR 46, and the FDA regulations at 21 CFR

56.108(b)(1) and 21 CFR 312.66. For device studies, part 812 uses the term unanticipated adverse device effect, which is defined in 21 CFR 812.3(s). Guidance from the regulatory agencies considers unanticipated problems to include any incident, experience, or outcome that meets ALL three (3) of the following criteria:

Unexpected in terms of nature, severity or frequency given (a) the research procedures that are described in the protocol-related documents, such as the IRB-approved research protocol and informed consent document; and (b) the characteristics of the subject population being studied;

AND

Related or possibly related to participation in the research (possibly related means there is a reasonable possibility that the incident, experience, or outcome may have been caused by the procedures involved in the research);

AND

Suggests that the research places subjects or others at greater risk of harm (including physical, psychological, economic, or social harm) than was previously known or recognized. Note: According to OHRP, if the adverse event is serious, it would always suggest a greater risk of harm.

Follow-up

All adverse events will be followed up according to good medical practices.

### 7.3 Steps to Determine If an Adverse Event Requires Expedited Reporting

Step 1: Identify the type of adverse event using the NCI Common Terminology Criteria for Adverse Events (CTCAE v4).

Step 2: Grade the adverse event using the NCI CTCAE v4.

Step 3: Determine whether the adverse event is related to the protocol therapy.

Attribution categories are as follows:

- Definite – The AE *is clearly related* to the study treatment.
- Probable – The AE *is likely related* to the study treatment.
- Possible – The AE *may be related* to the study treatment.
- Unlikely – The AE *may NOT be related* to the study treatment.
- Unrelated – The AE *is clearly NOT related* to the study treatment.

Note: This includes all events that occur within 30 days of the last dose of protocol treatment. Any event that occurs more than 30 days after the last dose of treatment and is attributed (possibly, probably, or definitely) to the agent(s) must also be reported accordingly.

Step 4: Determine the prior experience of the adverse event.

Expected events are those that have been previously identified as resulting from administration of the agent. An adverse event is considered unexpected, for expedited reporting purposes only, when either the type of event or the severity of the event is not listed in:

- the current known adverse events listed in the Agent Information Section of this protocol;
- the drug package insert;
- the current Investigator's Brochure
- the radiation therapy known toxicities section of this protocol

### 7.3.1 **Reporting SAEs and UPIRSOs to the Simmons Comprehensive Cancer Center (SCCC) Data Safety Monitoring Committee (DSMC)**

All SAE/UPIRSOs at all sites, which occur in research subjects on protocols for which the SCCC is the DSMC of record require reporting to the DSMC regardless of whether IRB reporting is required. All SAEs/UPIRSOs occurring during the protocol-specified monitoring period should be submitted to the SCCC DSMC within 5 business days of the PI or delegated study team members awareness of the event(s). In addition, for participating centers other than UTSW, local IRB guidance should be followed for local reporting of serious adverse events.

The UTSW study team is responsible for submitting SAEs/UPIRSOs to the SCCC DSMC Coordinator. Hardcopies or electronic versions of the eIRB Reportable Event report; FDA Form #3500A forms, or other sponsor forms, if applicable; and/or any other supporting documentation available should be submitted to the DSMC Coordinator. The DSMC Coordinator forwards the information onto the DSMC Chairman who determines if immediate action is required. Follow-up eIRB reports, and all subsequent SAE/UPIRSO documentation that is available are also submitted to the DSMC Chair who determines if further action is required. *(See Appendix III of the SCCC DSMC Plan for a template Serious Adverse Event Form which may be utilized when a sponsor form is unavailable and SAE submission to the eIRB is not required).*

If the event occurs on a multi-institutional clinical trial coordinated by the UTSW Simmons Comprehensive Cancer Center, the DOT Manager or lead coordinator ensures that all participating sites are notified of the event and resulting action, according to FDA guidance for expedited reporting. DSMC Chairperson reviews all SAEs/UPIRSOs upon receipt from the DSMC Coordinator. The DSMC Chairperson determines whether action is required and either takes action immediately, convenes a special DSMC session (physical or electronic), or defers the action until a regularly scheduled DSMC meeting.

The following instructions section may be modified as needed to ensure clear guidance for institutions participating in the trial who will not report directly to the UTSW Institutional Review Board. If needed, this reporting may be facilitated by the UTSW study team for example.

Telephone reports to: (Investigator/study team: Insert names and phone numbers for required notifications)

### **Reporting Unanticipated Problems Involving Risks to Subjects or Others (UPIRSOs) to the UTSW HRPP/IRB**

UTSW reportable event guidance applies to all research conducted by or on behalf of UT Southwestern, its affiliates, and investigators, sites, or institutions relying on the UT Southwestern IRB. Additional reporting requirements apply for research relying on a non-UT Southwestern IRB.

According to UTSW HRPP/IRB policy, UPIRSOs are incidents, experiences, outcomes, etc. that meet **ALL three (3)** of the following criteria:

1. Unexpected in nature, frequency, or severity (i.e., generally not expected in a subject's underlying condition or not expected as a risk of the study; therefore, not included in the investigator's brochure, protocol, or informed consent document), AND
2. Probably or definitely related to participation in the research, AND
3. Suggests that the research places subjects or others at a greater risk of harm (including physical, psychological, economic, or social harm) than was previously known or recognized. Note: According to OHRP, if the adverse event is serious, it would always suggest a greater risk of harm.

For purposes of this policy, UPIRSOs include unanticipated adverse device effects (UADEs) and death or serious injury related to a humanitarian use device (HUD).

UPIRSOs must be promptly reported to the UTSW IRB within 5 working days of PI awareness.

For research relying on a non-UT Southwestern IRB (external, central, or single IRB):

Investigators relying on an external IRB who are conducting research on behalf of UT Southwestern or its affiliates are responsible for submitting **LOCAL** UPIRSOs to the UT Southwestern IRB within 5 working days of PI awareness. Investigators must report to their relying IRB according to the relying IRB's policy. In addition, the external IRB's responses or determinations on these local events must be submitted to the UT Southwestern IRB within 10 working days of receipt.

Events NOT meeting UPIRSO criteria:

Events that do NOT meet UPIRSO criteria should be tracked, evaluated, summarized, and submitted to the UTSW HRPP/IRB at continuing review.

For more information on UTSW HRPP/IRB reportable event policy, see <https://www.utsouthwestern.edu/research/research-administration/irb/assets/policies-combined.pdf>.

#### **7.4 Stopping Rules**

Interim analysis will be performed after enrollment of 6 patients. The stopping rules for study includes grade 3 acute toxicity in >30% of enrolled patients, and tumor progression/growth in >50% of enrolled patients.

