**5.3 Follow-up Procedures**

Subject will be followed at every six months (+/- 2 weeks) thereafter for five years after their first follow up at 1 month (+/- 1 week).

With every visit, patients will have:

- Physical exam including: vital signs, weight, height and BMI
- MRI with or without contrast or CT with contrast
- Renal scintigraphy scan at 1 year
- Hematology
- Serum Chemistries
- Urine Analysis
- Lab corollary blood draw at 1 month and six month
- Performance status
- Toxicity evaluation
- Tumor measurements

**\*Note:** Subjects who show progressive disease or develop a new primary will be followed for survival only and will no longer strictly adhere to study calendar.

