#### **6.1.4 Response Criteria**

##### **6.1.4.1 Evaluation of Lesions**

Complete Response (CR): Disappearance of all target lesions. Disappearance of all target lesions. Any pathological lymph nodes (whether target or non-target) must have reduction in short axis to <10 mm (the sum may not be "0" if there are target nodes). Determined by two separate observations conducted not less than 4 weeks apart. There can be no appearance of new lesions.

Partial Response (PR): At least a 30% decrease in the sum of the longest diameter (LD) of target lesions, taking as reference the baseline sum LD. There can be no appearance of new lesions.

Progressive Disease (PD): > 20% increase in the SLD taking as reference the smallest SLD recorded since the treatment started (nadir) and minimum 5 mm increase over the nadir.

Stable Disease (SD): Neither sufficient shrinkage to qualify for PR nor sufficient increase to qualify for PD, taking as reference the smallest sum LD since the treatment started. There can be no unequivocal new lesions.

Tumor Growth (TG): At least a 4mm increase in the LD of treated lesion in a single scan when compared to baseline scan (or an increase of >2.0mm in two consecutive scans).

Local Control: No TG AND a complete radiographic or pathologic absence of tumor viability.

Local Failure: Any TG OR any radiographic or pathologic evidence of tumor viability.

Indeterminate Disease Response: (IDR): 1) Presence of radiographic evidence of viable disease without any increase in the LD (<4mm) sufficient enough to qualify for TG; 2) complete absence of radiographic evidence of viable disease regardless of any change in tumor diameter.

A biopsy is recommended in the case of tumors with ≥4mm increase in size with no radiographic evidence of viable tumor, OR any tumors with radiographic evidence of viable tissue.

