### 7.2.1 **Definition**

An adverse event is defined as any untoward or unfavorable medical occurrence in a human research study participant, including any abnormal sign (for example, abnormal physical exam, imaging finding or clinically significant laboratory finding), symptom, clinical event, or disease, temporarily associated with the subject's participation in the research, whether or not it is considered related to the subject's participation in the research.

Adverse events encompass clinical, physical and psychological harms. Adverse events occur most commonly in the context of biomedical research, although on occasion, they can occur in the context of social and behavioral research. Adverse events may be expected or unexpected. **Acute Adverse Events**

An adverse event is defined as any untoward or unfavorable medical occurrence in a human research study participant, including any abnormal sign (for example, abnormal physical exam or laboratory finding), symptom, clinical event, or disease, temporarily associated with the subject's participation in the research, whether or not it is considered related to the subject's participation in the research. Adverse events occurring through the time period of [the start of treatment through the first follow up occurring 12 weeks post treatment](#) will be considered acute adverse events. All acute adverse events will be assessed and reported as per below.

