## 9.0 STATISTICAL CONSIDERATIONS

### 9.1 Study Design/Study Endpoints

This is an open label single-arm phase II non-randomized prospective single arm study that treats a single SRM with SABR. The primary objective is local control of the SRMs. Local control is defined as less than 4mm increase in the longest diameter of tumor measured using either MRI or contrast enhanced CT scan and with no radiographic or pathologic evidence of viable tumor. The endpoint will be measured at a minimum follow up of one year. Secondary objections and endpoints explore the safety, toxicity, growth, growth rate, local failure, IDR, immune response and progression of the SRMs after SABR.

The stopping rules for this study include any treatment-related >grade 3 toxicity. If there are any treatment related grade 3 acute toxicity in >30% of enrolled patients after enrollment of at least 6 patients, the study will be suspended until permitted by a safety review.

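### Sections 7.4 and 9.1 state the acute toxicity stopping rule differently, and the growth rule in 7.4 is keyed to enrolment of 6, so patients not yet scanned count as not growing

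*Protocol*

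**What the plan says.** All references are to the protocol.

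- **Section 7.4.** "Interim analysis will be performed after enrollment of 6 patients". The rule that follows "includes grade 3 acute toxicity in >30% of enrolled patients, and tumor progression/growth in >50% of enrolled patients". It requires no attribution to treatment and does not say what happens when a limit is crossed.
- **Section 9.1.** "The stopping rules for this study include any treatment-related >grade 3 toxicity". A second condition reads: "If there are any treatment related grade 3 acute toxicity in >30% of enrolled patients after enrollment of at least 6 patients". The consequence given for that condition is that "the study will be suspended until permitted by a safety review". The section has no growth rule.
- **Section 7.2.1.** Acute adverse events are those from "the start of treatment through the first follow up occurring 12 weeks post treatment".
- **Sections 5.3 and 5.4.** Visits are every six months "for five years after their first follow up at 1 month (+/- 1 week"). Toxicity is evaluated at one month and then six-monthly. MRI or CT appears at baseline and six-monthly, not at one month. There is no 12-week visit.
- **Appendix B.** The RTOG acute criteria run from the start of therapy to day 90.
- **Section 6.1.4.1.** Tumour growth is "At least a 4mm increase in the LD of treated lesion in a single scan when compared to baseline scan", or more than 2.0 mm on two consecutive scans.

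**The concern.** A stopping rule should give one answer for one set of data. Here the same 30% limit appears twice with different events counted, different timing and a consequence in only one place. The people applying it could reach different decisions and each point to the protocol.

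The growth rule has a different weakness. Its numerator can come only from patients with a post-treatment scan, while its denominator is everyone enrolled and its timing follows enrolment. A patient whose first scan is still months away is counted as not growing. The safeguard can then look satisfied because data are missing rather than because tumours are controlled.

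**Working it through.** The protocol gives no operating characteristics for these rules, so there is no stated figure to reproduce.

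**1. Toxicity rule, side by side**

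| | 7.4 | 9.1 |
|---|---|---|
| Grade 3 acute limit | >30% of enrolled | >30% of enrolled |
| Attribution | none required | treatment-related |
| Timing | interim analysis after 6 | from at least 6 onward |
| Consequence | not stated | suspension until safety review |
| Above grade 3 | not mentioned | any treatment-related event |
| Growth | >50% of enrolled | not mentioned |

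With 6 patients, 0.30 × 6 = 1.8, so the limit is crossed at 2 events (2/6 = 33%). Two unrelated grade 3 acute events cross it under 7.4. Under 9.1 the count is 0/6 and nothing is triggered.

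**2. Acute window**

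Section 4.2.3 allows treatment to run to 21 days. Twelve weeks after the end of treatment is 84 days, so the 7.2.1 window can close at day 21 + 84 = 105, against day 90 in Appendix B. Neither date is a scheduled visit. The first scheduled follow-up is at one month, not 12 weeks.

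**3. Growth rule: count needed**

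0.50 × 6 = 3, and more than 3 means at least 4 of 6. If s of the 6 have been scanned, at most s can be counted as growing. For s ≤ 3 the rule cannot be met.

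**4. How many are scanned at the sixth enrolment**

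Assumptions, because accrual is not stated: 16 patients accrue evenly over Y years, so the gap between patients is g = 12Y/16 months. Treatment takes 0.75 month (about the 21-day maximum). The first scan is 6 to 7 months later, depending on how the six-monthly interval after the one-month visit is read. Patient i then has (6 − i) × g months since enrolment and needs 6.75 to 7.75 months to have been scanned.

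| Accrual of 16 over | g (months) | Scanned, of 6 |
|---|---|---|
| 1 year | 0.75 | 0 |
| 1.5 years | 1.125 | 0 |
| 2 years | 1.5 | 0–1 |
| 3 years | 2.25 | 2–3 |
| 4 years | 3.0 | 3 |
| 5 years | 3.75 | 3–4 |

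The fourth patient is scanned only if 2g ≥ 6.75 to 7.75, so g ≥ 3.375 to 3.875 months, which is 4.5 to 5.2 years to accrue 16. The Study Summary gives a 5-year duration and 9.1 a minimum of one year of follow-up, which suggests 4 years as a natural upper limit for accrual. The sixth patient has no post-treatment scan at enrolment under any accrual rate.

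**5. Effect on triggering**

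Take assumed growth rates above the rule's own limit, with growth visible on the scan in hand:

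- All 6 scanned: P(at least 4 of 6) = 0.74 at a rate of 70% and 0.98 at 90%.
- 4 scanned: all four must have grown, so 0.7⁴ = 0.24 and 0.9⁴ = 0.66.
- 3 or fewer scanned: 0 at any rate.

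**The case against.** Both sections introduce their rules with an open-ended verb, so the lists can be read as additive. On that reading the trigger above grade 3 in 9.1 and the growth trigger in 7.4 both apply, and neither omission is a contradiction. This stands. A reader might infer that one related grade 4 event stops the trial under 9.1 but not under 7.4; that follows only if 7.4 is taken as exhaustive, which it does not claim to be. The additive reading does not remove the attribution mismatch, because there the same limit is stated in two incompatible ways.

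A reader might also take the conjunction in 7.4 to require both limits at once. The plural heading, the separate thresholds and the stand-alone use of the toxicity limit in 9.1 make two independent rules the more natural reading. A clarifying phrase would settle it.

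On growth, a reader might conclude that the needed scans cannot exist at the look. The documents do not support that. The wording places the look after the sixth enrolment without fixing a day, accrual is unstated, and slow accrual could give 3 or 4 scanned patients. Nor does the protocol say that growth is never examined again. Section 10.5 provides real-time review of serious events, quarterly review of adverse events and annual trial review. For individual patients, Section 1.3 offers standard care at any sign of progression and 6.1.4.1 recommends biopsy in defined cases. These protect patients, but they do not make the trial-level growth rule computable.

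Finally, a toxicity count needs onset dates, not a visit on the closing day, so the missing 12-week visit is secondary. The differing closing dates remain.

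**Conclusion.** The point holds in this form. The >30% grade 3 acute toxicity rule is stated inconsistently in attribution, timing and consequence, and two unrelated events in 6 patients are enough to give opposite answers. The full set of stopping rules is written in neither section, and the acute window has two definitions, neither aligned with a visit. These findings rest on the text alone.

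The growth rule is wrong as written because it treats unscanned patients as not growing. It needs 4 of 6 and cannot be met with 3 or fewer scanned. That this would be so at the sixth enrolment is conditional: it holds for even accrual of 16 over 4 years or less, with first scans on schedule and no earlier unscheduled imaging. It may not hold over 5 years or if the look is taken later.

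Low triggering chances at a true growth rate of exactly 50% (0.34 with all 6 scanned) might be offered as further evidence. They are not, because 50% does not exceed the rule's own limit.

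**What to change.** 1. The investigators and the safety committee should reconcile 7.4 and 9.1, together with the acute window in 7.2.1, the schedule in 5.3 and 5.4, and Appendix B, into one set of rules with the same grades, attribution, window, timing and consequence. No clinical content is proposed here.
2. State that each criterion applies on its own, if that is the intent.
3. Compute the growth proportion among patients with at least one post-treatment scan, and tie the growth assessment to the number of scanned patients. Keep it separate from the toxicity look, which need not wait.

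This is a wording amendment. It needs no extra visits provided the acute window is aligned with an existing contact. The cost is calendar time. If the growth assessment waits for 6 scanned patients, it falls 6.75 to 7.75 months after the sixth enrolment under the assumptions above. At one-year accrual (g = 0.75) a further 9 to 10 patients enrol in that time (6.75/0.75 = 9; 7.75/0.75 = 10.3), so 15 to 16 of 16 are already in. At four-year accrual (g = 3) it is 2 more, so 8 of 16. The number of scanned patients that triggers the assessment should be chosen with that in view. The two-consecutive-scan form of growth in 6.1.4.1 will still be unassessable in patients with one scan, and the rule should say so.
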